6.1.4.6. Father and mother's highest education

Education level is categorized as:

- High education Yes: Higher education/University (educational program more than 3 years), and Higher education (educational program 3 years or less)
- No: Secondary school and less than secondary school

6.1.4.7. Number of people living in the household at month 3

Number of people living in the household are categorized as

- 1-3, inclusive
- 4-6, inclusive
- ≥7

6.1.4.8. Number of children (< 18) living in the household at month 3

Number of children living in the household are categorized as:

- 0
- 1-2, inclusive
- ≥ 3 ,

6.1.4.9. Other

- Age of the subject at time of the LRTI case will be expressed in months and will be computed as the difference between the start date of the LRTI case and the date of birth.
- Age of the subject at time of blood sample collection will be expressed in months and will be computed as the difference between the sample collection date and the date of birth.
- Age of the mother at the time of childbirth will be expressed in years and will be computed as the difference between the birth date of the subject and the birth date of the mother.
- Duration of the study for each subject will be computed as the difference between the date of last contact (i.e., active or passive surveillance contact or the date of the censoring) and the date of enrolment (date when ICF was first signed by the subject's parent[s]/LAR[s]).

6.2. Data Presentation

The following decimal description will be used for the analyses.

Table 11Decimal points in analyses

Display Table	Parameters	Number of decimal digits
All summaries	% of frequency, including LL & UL of CI	1
All summaries	% frequency, including LL & UL of CI	1
All summaries	Mean, median, minimum, maximum	1
All summaries	SD	2
All summaries	P -value	3

6.3. Subgroup definition

Sub-group order in tables	Sub-group label in tables	Sub-group definition for footnote
Country		
1	AR	Subjects from Argentina
2	BD	Subjects from Bangladesh
3	CA	Subjects from Canada,
4	FI	Subjects from Finland
5	HN	Subjects from Honduras
7	SA	Subjects from South Africa
8	TH	Subjects from Thailand
9	US	Subjects from US
Age category		
1	0-5M	0 - < 6 months
2	6-11M	6 - < 12 months
3	0-11M	0 - < 12 months
4	12-17M	12 - < 18 months
5	18-23M	18 - < 24 months
6	12-23M	12 - < 24 months
7	0-23M	0 - < 24 months
Monthly age cate	gory	
1	0M	Less than 1 month of age
2	1M	1 - < 2 month of age
3	2M	2 - < 3months of age
4	3M	3 - < 4 months of age
5	4M	4 - < 5 months of age
6	5M	5 - < 6 months of age
Birth period		
1	Born during the transmission season	Born during the transmission season
2	Born out of the transmission season	Born out of the transmission season
Follow up in trans	smission season in first 6 month of life	
1	≤3 months	≤3 months of life in transmission season
2	>3 months	>3 months of life in transmission season
Sub-cohort group	DS	
1	BS 2M	Subjects with blood sample at 2 months
2	BS 4M	Subjects with blood sample at 4 months
3	BS 6M	Subjects with blood sample at 6 months
4	BS 12M	Subjects with blood sample at 12 months
5	BS 18M	Subjects with blood sample at 18 months
6	BS 24M	Subjects with blood sample at 24 months

The following sub-group names will be used for the statistical analyses:

Statistical Analysis Plan Amendment 1 Final

Tables will, in general, be displayed by study group for descriptive tables and for incidence computation.

Please note that age intervals are overlapping as we are interested to calculate endpoints also during the first and second year of life.

6.4. General considerations calculations of incidence

When mentioned below in the upcoming analyses sections, analysis by subgroups will include:

- Country
- Age interval:
 - 0-5M
 - 6-11M
 - 0-11M
 - 12-23M
 - 0-23 M
- Age interval by months for the first 6 months

6.5. Analysis of demographics/baseline characteristics

The distribution of subjects enrolled among the study sites will be tabulated at least overall and by country. The distribution of subjects of the PPS sub-cohort will be described for the various time points.

The demographic, medical status, family history, lifestyle characteristics, medical care and medications collected for the enrolled subjects will be summarized at least overall.

The surveillance visit and examination visit information, and the laboratory results will be described:

- Frequency tables will be generated for categorical variable such as country.
- Mean, median, standard deviation will be provided for continuous data such as age.

6.6. Incidence analysis

6.6.1. Analysis of co-primary objectives: incidence of RSV respiratory disease

For this objective, the analysis will be based on PPS.

For clarity the analysis of RSV disease incidence is summarised in the table below showing endpoints and analytic methods.

200150 (EPI-RSV-005 BOD)

Statistical Analysis Plan Amendment 1 Final

For each of the following endpoints you could find the case definitions in Table 4:

- RSV RTI with suspicion of involvement of LRT
- WHO RSV LRTI
- WHO RSV LRTI hospitalisation
- WHO RSV severe LRTI
- WHO RSV severe LRTI hospitalisation
- WHO RSV hospitalisation

Table 12Summary of RSV incidence analyses for primary objectives

Endpoints	Incidence analysis method	Subgroup
RSV RTI with suspicion of involvement of LRT WHO RSV LRTI WHO RSV severe LRTI RSV hospitalisation WHO RSV LRTI hospitalisation WHO RSV severe LRTI hospitalisation	Incidence rates of first episode Cumulative probability of first episode (Kaplan Meier)	Overall, by country, by age intervals, by transmission interval
RSV RTI with suspicion of involvement of LRT WHO RSV LRTI WHO RSV severe LRTI RSV hospitalisation WHO RSV LRTI hospitalisation WHO RSV severe LRTI hospitalisation	Proportion affected by all new episodes	Overall and by country, by age intervals
RSV RTI with suspicion of involvement of LRT WHO RSV LRTI WHO RSV severe LRTI RSV hospitalisation WHO RSV LRTI hospitalisation WHO RSV severe LRTI hospitalisation	Incidence proportion of first episode	Overall and by country, by monthly age

For each endpoints listed in the previous table the 95% CI will be computed as described in section 11.1.2 depending on the age category considered and the method listed in the analysis column. Kaplan-Meier curves presenting the cumulative probability of first episode will be displayed overall and by country. The cumulative probability of presenting first episode will be given with its 95% CI at the end of the follow-up.

6.6.2. Analysis of secondary objective: incidence of all cause respiratory disease

The analysis will be based on PPS and will be done on the first episode of all cause RTIs occurring during the age interval considered.

200150 (EPI-RSV-005 BOD)

Statistical Analysis Plan Amendment 1 Final

The incidence will be computed overall and by age category:

- 0-5 months
- 6-11 months
- 0-11 months
- 12-23 months
- 0-23 months

Incidences rates will be calculated using the same approach describe in section 11.1.1 for first episode of RTI with a suspicion of involvement of the lower respiratory tract, WHO LRTI and WHO severe LRTI and LRTI hospitalization.

6.6.3. Analysis of tertiary objectives: potential risk factors for RSV disease

For this objective, the analysis will be based on PPS.

The incidence, overall and by country, of first events of RSV-LRTI, RSV severe LRTI, RSV non severe LRTI (WHO definition) will be analysed using a Cox regression.

The following risk factors will be considered in the model:

- General:
 - Country of birth
 - Gender (as recorded in demography of extension phase)
 - Time of birth relative to the transmission season (see section 6.1.4.5)
- Characteristics at birth:
 - Gestational age at birth (see details section 6.1.4.1)
 - Birth weight (see details section 6.1.4.2)
 - Apgar at 5 mins of age (see details section 6.1.4.3)
 - Caesarian section
- Family history:
 - First degree relative with family history of asthma (see details section 6.1.4.4)
- Living environment and household composition:
 - Highest education level of the mother (see details section 6.1.4.6)
 - Highest education level of the father (see details section 6.1.4.6)
 - Number of people living in the household at month 3 (see details section 6.1.4.7)
200150 (EPI-RSV-005 BOD)

- Statistical Analysis Plan Amendment 1 Final
- Number of other children (<18 years old) living in the household at month 3 (see detail section 6.1.4.8)
- Subject in regular close contact with toddlers at month 3
- The child live in a surrounding where people smoke daily at month 3
- Breast feeding *

* Time dependent covariate; status is yes of subject ever breastfed from DOB until the end of breastfeeding given in the surveillance visit. Last day of month will be imputed for any partial date of breastfeeding end date.

As described in the section 11.1.5, covariates with univariate p-value less than 0.1 will be included in the multivariable model. The number of covariates included in the model will depend on the number of events (at least 10 events per covariates).

Please note that the multivariable model will be performed only if the number of events is sufficient (at least 10 events per covariates). In addition, depending on the data, other models could be explored or the model could be simplified.

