5.3.1. Primary study (from birth up to the age of 2 years)

Before birth:

- Subject whose parent(s)/LAR(s), in the opinion of the investigator, can and will comply with the requirements of the protocol (e.g., sample collection, availability for examination visits).
- Written informed consent (or witnessed thumb printed consent in case of an *illiterate subject)* (including consent to obtain a cord blood sample at birth) obtained from the parent(s)/LAR(s) of the subject

After Birth:

- Subject for whom updated and re-signed informed consent and confirmation of eligibility is available not later than 5 working days after birth.
- Cord blood sample collection of at least 3 mL, at birth.

5.3.2. Extension Study (from the age of approximately 2 years up to the 6th birthday)

- Subject is enrolled at a study site that is participating in the extension period follow-up.
- Subject whose parent(s)/LAR(s), in the opinion of the investigator, can and will comply with the requirements of the protocol (e.g., availability for quarterly contacts).
- Written informed consent *(or witnessed thumb printed consent in case of an illiterate subject)* obtained from the parent(s)/LAR(s) of the subject.
- Previous participation in the primary study (from birth up to the age of 2 years).

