6.4.2. Extension Study (approximately 2 years of age up to the 6th birthday)

 Table 8 presents the list of procedures for the extension study.

Note that although extension study enrolment ideally occurs at the time of the subjects' second birthdays, enrolment into, and first contact for, the extension study may take place at any time between the end of the primary study and the subject's 6th birthday.

After the first extension study contact, subjects will be contacted around the time of each subject's birthday and (approximately) quarterly during the intervals between (a) first contact and next birthday; (b) subsequent birthdays.

Site staff may contact subjects more frequently than indicated in Table 8 if *consistent with the language of the local ICF* and considered necessary by the study physician. Parents will be encouraged to seek a clinical assessment of their child in between quarterly contacts and/or during quarterly contacts whenever their child develops wheezing and/or breathing difficulties.

Refer to Section 6.6 and the SPM for additional details.

200150 (EPI-RSV-005 BOD)

Protocol Amendment 3 Final

Table 8List of extension study procedures (from the age of approximately 2 years up to the 6th birthday) (Amended 15-
DEC-2017)

Epoch 2	Data collection				
Visit/Contact	First Contact a	Quarterly Contact ^{b, c}	Annual contact ^{, c, d}		
Time points	Extension study enrolment		Around the 2 ^d , 3 rd , 4 th , 5 th , and 6 th birthdays (+ 3 months)		
Perform / document results of these procedures					
Informed consent for extension	•				
Check inclusion/exclusion criteria for extension	•				
Collect demographic data for extension	•				
Collect data on potential symptoms and risk factors for wheeze and asthma	•	• (applies to Version 1.0 of the quarterly contact script)	• d		
Record episodes of wheeze, asthma, and troublesome lungs	•	•	● d		
Collect data about medication used to treat asthma, wheeze, or troublesome lung symptoms	•	•	● d		
Review / assess information about asthma diagnoses and medication use based on medical record abstraction and subject information over approximately the past 12 months or longer	• e		• e		
Interim analysis after 4th birthday; Final analysis after 6th birthday			•		
Investigator sign-off on eCRF before analysis			● f		
Study conclusion for extension			• g		
and enter data into these eCRF modules					
	 First Contact Annual ^a 	• Quarterly	QuarterlyAnnual		

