6.5.7. Collection of medical history, demographic and lifestyle characteristics

Obtain the family medical history, demographic and lifestyle characteristics of the subject as required by the eCRF, by interviewing parent(s)/LAR(s) and/or reviewing the medical records and record data collected in the subject's eCRF. This includes family history of respiratory disease, living environment and household composition, breastfeeding, passive smoking and day-care attendance.

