6.5.8. Collection of data on child at birth and delivery

Information about the delivery and the newborn (including medical care provided immediately after birth and planned to be provided subsequently) should be collected from the parents/LAR and completed and/or confirmed from an original source accessed through a person involved in the delivery of the subject or from any authorized person representing the healthcare organization that is in charge of the source and the collected data should be recorded in the subject's eCRF.

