6.6.3. Collection of demographic data

Record gender and ethnicity in the subject's eCRF.

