11.1.5. Cox regression models

Cox regression models will be performed for the univariate analyses in order to obtain unadjusted hazards ratios of the determinants of interest.

200150 (EPI-RSV-005 BOD)

Statistical Analysis Plan Amendment 1 Final

In addition, a multivariable Cox regression model will be performed in order to estimate the relative contribution of each potential risk factor adjusting for the simultaneous effects of the other covariates. The model will include: time-independent covariates (e.g., country, gender etc.) and time-dependent covariates, breast feeding. Covariates selection will be done using statistical significance. Potential risk factors will be included in the multivariable models if univariate p-value will be less than 0.1.

The Table 15 details the time dependent status of the potential risk factors:

Table 15Time dependent status of the covariates

Potential risk factor	Time-dependent
Country of birth	No
Gender	No
Birth period	No
Gestational age at birth	No
Birth weight	No
Apgar at 5 mins of age	No
First degree relative with family history of asthma	No
Quartiles of cord blood maternal antibodies for RSV A	No
Quartiles of cord blood maternal antibodies for RSV B	No
Highest education level of the mother	No
Highest education level of the father	No
Number of people living in the household at month 3	No
Number of other children (<18 years old) living in the household at month 3	No
Subject in regular close contact with toddlers at month 3	No
The child live in a surrounding where people smoke daily at month 3	No
Breast feeding	Yes

Results from the multivariable Cox model will include hazards ratios (with 95% CI).

The number of covariates included in the model will depend on the number of events (at least 10 events per covariates).

Please note that the multivariable model will be performed only if the number of events is sufficient (at least 10 events per covariates). In addition, depending on the data other models could be explored or the model could be simplified.

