												. 4	.00130		1-130	v-(100 DC)))
									Stat	isti	cal An	aly	sis Pla	n A	\mend	me	nt 1 Fi	nal
	Total		AR		BD		CA		FI		HN		SA		TH		US	
	N =		N =		N =		N =		N =		N =		N =		N =		N =	
	Value	%	Value	%	Value	%	Value	%	Value	%								
	orn		orn		orn		orn		or n		or n		orn		orn	1	orn	
Maximum																		
Missing																		
Subiect in																		
regular close																		
contact with																		
toddlers at																		
Month 3																		
Yes																		
No																		
Missing																		
The child live																		
in a																		
surrounding																		
where people																		
smoke daily at																		
Month 3																		
Yes																		
No																		
Missing						1		1										

N = total number of subjects

n/% = number / percentage of subjects in a given category

Value = value of the considered parameter

SD = standard deviation

AR = Argentina

BD = Bangladesh

CA = Canada

FI = Finland

HN = Honduras

SA = South Africa

TH = Thailand

US = US

Transmission season:

October to March for Argentina, South Africa;

April 2014 to September 2014 for Canada, Finland, United states;

All year long for Bangladesh, Honduras, Thailand

Note:

Gender information reported herein was collected during the ongoing extension study, causing some missing data Breastfeeding duration was provided for subjects who breastfed

200150 (EPI-RSV-005 BOD)

Statistical Analysis Plan Amendment 1 Final

Template 5 Summary of demographic characteristics of subjects with blood sample – overall and by time point (PPS sub cohort)

	Mont N =	h 2	Month N =	า 4	Month N =	6	Month N =	12	Month N =	18	Month N =	24
	n	%	n	%	n	%	n	%	n	%	n	%
Country												
Argentina												
Bangladesh												
Canada												
Finland												
Honduras												
South Africa												
Thailand												
US												
Gender of new born												
Male												
Female												
Missing												
Gestational age at birth (weeks)												
≤ 28												
29-32												
33-36												
≥ 37												

N = total number of subjects at each timepoint

n/% = number / percentage of subjects in a given category

Value = value of the considered parameter

Note:

Gender information reported herein was collected during the ongoing extension study, causing some missing data

Template 6 Number of subjects by center (Total enrolled cohort)

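### Sex is taken from extension enrolment but offered as a baseline covariate for RSV LRTI at 0-2 years, so whether it is known is decided after the outcome, and the SAP has no rule for missing sex

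*SAP*

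**What the plan says.** SAP 6.6.3 lists the candidate covariates for Cox models of first RSV LRTI, severe LRTI and non-severe LRTI (WHO definition). Sex appears as "Gender (as recorded in demography of extension phase". The note under Templates 4 and 5 (SAP 12.2.1) concedes the consequence: "Gender information reported herein was collected during the ongoing extension study, causing some missing data".

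In the protocol, the instruction "Record gender and ethnicity in the subject's eCRF" stands in section 6.6.3, among the extension procedures. The birth-visit section (6.5.7) refers to demographic data as the eCRF requires and then specifies: "This includes family history of respiratory disease, living environment and household composition, breastfeeding, passive smoking and day-care attendance". Sex is not named there.

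Entry to the extension needs new parental consent and past participation in the primary study. A further criterion reads "Subject is enrolled at a study site that is participating in the extension period follow-up" (protocol 5.3.2). A child in care is excluded (5.4.2). On timing, protocol 6.4.2 says that "enrolment into, and first contact for, the extension study may take place at any time between the end of the primary study" and the sixth birthday.

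The outcome windows are earlier: 0-2 years in Template 17, and 0-2 and 0-5 months in SAP 6.9.1 (Templates 43-45), where sex is an optional covariate. Selection is automatic: "Potential risk factors will be included in the multivariable models if univariate p-value will be less than 0.1" (SAP 11.1.5), subject to at least 10 events per covariate. All four Cox templates give gender a 'Missing' row beside columns for events, hazard ratio, p-value and global p-value. The notes to Templates 43-45 exclude children with missing cord-blood values. No rule is given for missing sex, and SAP section 9 (changes from planned analyses) does not mention it.

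**The concern.** Sex is fixed at birth, but in this dataset whether it is known is settled only after the outcome window has closed. It can depend on drop-out, death, refusal, child-in-care status, belonging to a site outside the extension, or not yet being enrolled in an extension that was still running. Some of these may be related to having had an RSV LRTI: parents of a child who had one may be more or less willing to join a wheeze and asthma follow-up. Others may be related to country, and so to the RSV rate.

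Two analyses are open to the programmer, and neither is safe by default. If 'Missing' is fitted as a third level, later participation helps to predict an earlier event, and gender can be selected for that reason alone. If children with missing sex are dropped, the models lose children and events while the 10-events rule still applies. At stake are the tertiary risk-factor model and one optional covariate in the secondary cord-antibody model.

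**Working it through.** **1. The plan's own figures.** Protocol 9.3 assumes about 20% drop-out. 1920 / (1 - 0.20) = 2400, and 320 / 0.80 = 400 per country or region; both match the plan.

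**2. How much sex could be missing.** If drop-outs do not later enter the extension, 2400 - 1920 = 480 children (20%) lack sex. Adding an assumed refusal of 15% gives 0.20 + 0.80 x 0.15 = 32%; at 40% it gives 0.20 + 0.80 x 0.40 = 52%. The documents give no refusal rate.

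**3. Effect on the Cox models.** Simulation with 2400 children and 300 runs per scenario. From protocol 9.3: 20% drop-out, and a first-year RSV LRTI rate of 20 x 8 = 160 per 1000 child-years. Assumed: second-year rate 30 per 1000, antibody hazard ratio (HR) 0.74 per SD, sex independent of antibody level, refusal 15% unless stated, and the odds ratio (OR) of refusing after an RSV LRTI. Screening used the 2-df global Wald test of male and 'Missing' in a univariate model. The HRs come from a model that also contains antibody.

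| Scenario | Sex missing | 'Missing' HR | Male HR, 'Missing' as level / complete-case | Gender passes p<0.1 |
|---|---|---|---|---|
| No sex effect, OR 1 | 32% | 1.00 | 1.00 / 1.00 | 8% |
| No sex effect, OR 0.5 | 31% | 0.75 | 0.99 / 0.99 | 71% |
| No sex effect, OR 2 | 34% | 1.47 | 1.01 / 1.01 | 95% |
| No sex effect, OR 2, refusal 40% | 54% | 1.71 | 1.00 / 0.99 | 100% |
| No sex effect, one of 8 countries outside, rate x 2 | 40% | 1.33 | 1.00 / 1.00 | 81% |
| No sex effect, one of 8 countries outside, rate x 0.5 | 40% | 0.83 | 1.01 / 1.01 | 46% |
| True male HR 1.25, OR 2 in boys only | 33% | 1.30 | 1.09 / 1.09 | 64% |

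The antibody HR was 0.74-0.75 in every scenario, under both fits.

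**4. A second set of assumptions.** 2000 children, hazard 0.10 per year, 20% drop-out, no sex effect, 150 runs. Re-consent with/without an event of 0.6/0.6 selects gender in 13% of runs ('Missing' HR 0.99); 0.7/0.6 in 87% (0.73); 0.8/0.6 in 100% (0.50).

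**5. Events per covariate.** Take the 0-5 month hospitalization range in protocol 9.3 (16.9-44.1 per 1000 child-years) as a stand-in for severe LRTI, which is an assumption. With 2400 children:
- 0-2 months: 2400 x 0.25 x 0.0169 = 10 events, up to 2400 x 0.25 x 0.0441 = 26.
- 0-5 months: 2400 x 0.5 x 0.0169 = 20 events, up to 2400 x 0.5 x 0.0441 = 53.

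That allows one to five covariates. If 20% of events go with the excluded children, the ranges become about 8-21 and 16-42. At the low end the 0-2 month severe model no longer qualifies for a single covariate.

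**The case against.** **Timing alone does no harm.** A reader might infer that using a covariate recorded after the outcome biases these Cox models as such. It does not. With missingness unrelated to RSV LRTI, every estimate was correct and selection was near the nominal 10%. The male/female HR moved only when missingness depended on sex and outcome together (1.25 to 1.09).

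**The cord-antibody result is not shown to be biased.** A reader might infer that the secondary antibody HRs inherit the problem. They stayed at their set value in every scenario tested, all of which assumed sex independent of antibody level.

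**'Missing' rows are table shells.** Country of birth has one too, and no text says that the level enters the likelihood or the global p-value. That stands. But the SAP does not say the opposite either, and the screen does not say which of the two printed p-values it uses.

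**'Missing' is not simply the drop-outs and deaths.** Extension entry requires participation in the primary study, not completion, and is open until the sixth birthday. Drop-outs may therefore still enter, and some children may merely be late. The documents report no deaths and name no site outside the extension.

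**The size rests on assumptions.** The refusal odds ratios, re-consent gaps and country rate ratios have no source in the documents, and the SAP speaks only of some missing data. Country is also a candidate covariate, so a multivariable model that includes it would absorb that part of the problem; the univariate screen would not.

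**Scope is small.** The SAP calls its analyses descriptive and allows these models to be simplified. Also, the eCRF is not among the documents, so the reading that sex was collected only in the extension rests on protocol 6.6.3, SAP 6.6.3 and the template note.

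**Conclusion.** The point holds as a defect in covariate source and missing-data handling, not as a demonstrated bias in the main hazard ratios. Whether sex is known depends on events after the outcome window, the SAP acknowledges the gap, and it specifies nothing to deal with it. Under the assumed refusal and country differences, gender would be selected with no sex effect in 46-95% of runs at 31-40% missing, with a 'Missing' HR between 0.75 and 1.47 that has no interpretation. Complete-case fitting loses about 20% of children if planned drop-outs do not re-enter, and more with any refusal; the early severe-LRTI models can least afford this. Incidence, healthcare use and case-definition agreement do not use sex and are unaffected. It is worth correcting before the models are run, because the remedy is cheap.

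**What to change.** Obtain sex at birth for every enrolled child, where consent allows, through one data query to the source in protocol 6.5.8, which covers "Information about the delivery and the newborn (including medical care provided immediately after birth and planned to be provided subsequently"). Use that field in SAP 6.6.3, 6.9.1 and Templates 4, 5, 17 and 43-45. Section 6.5.8 does not name sex, so its availability at that source should be confirmed with sites. For withdrawn children (protocol 8.2), check first that consent covers a later query.

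Where sex cannot be retrieved, state in the SAP that:
- gender's selection p-value rests on the male/female contrast only;
- 'Missing' is never fitted as a level;
- children are not dropped for missing sex: either sex is multiply imputed, with event status, follow-up time and country in the imputation model, or gender is left out of the multivariable model;
- missing sex is tabulated by country and reason.

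Imputation would not repair the case where missingness depends on sex and outcome jointly; only retrieval does. The cost is one retrospective query per child or, under the fallback, a less precise or absent sex HR.
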